5.4. Screening Measures

Those who consent will be screened for eligibility using the following measures:

The following physiological measures will be collected and entered directly into REDCap by the interviewer:

- 1) Expired breath carbon monoxide (CO) levels will be assessed using an ico Smokerlyzer Smartphone Monitor (Covita -for remote collection) or a Bedfont CO monitor (for curbside collection), a reliable and valid measure of recent smoking.
 - a. Urinary cotinine test strips will be used to asses cotinine levels if a participant's carbon monoxide reading is less than or equal to 8 ppm.
- 2) A urine or saliva toxicological screen will be performed to assess the presence of illicit drugs including up to the following drugs: marijuana, cocaine, opiates, oxycodone, benzodiazepines, barbiturates, amphetamines, methadone, buprenorphine, methamphetamines, MDMA and PCP. Participants who fail the drug screen for drugs other than marijuana or their prescribed opioid medication may reschedule the interview but will need to be re-consented to ensure they have received adequate informed consent. They will be excluded if they are positive for drugs (other than marijuana or prescribed medications as determined by PI on a case-by-case basis) the second time.
- 3) Urine Pregnancy Test (HCG detection) will be performed for all participants.
- 4) Blood pressure and heart rate will be measured using an automated blood pressure monitor and a finger pulse oximeter to help the licensed medical professional determine final participant eligibility. Participants will be told if their blood pressure is in an abnormal range and advised to see a doctor by research staff. The research staff will also submit a medical event form for the LMP to review along with a Blood Pressure and Heart Rate Symptom Checklist form to ascertain details of the symptomatology for the LMP to review. In severe cases, the LMP may also choose to call the participant to follow-up and/or withdraw the participant from the study if necessary. All of these procedures are documented in our Blood Pressure/Heart Rate Collection: Standard Operating Procedure form which we can submit to the IRB if the Committee deems necessary.
- 5) Body temperature, respiratory rate and oxygen saturation will be added as physiological measures based on the CDC recommendations and those of [name].

https://www.cdc.gov/tobacco/basic_information/e-cigarettes/severe-lung-disease/healthcare-providers/index.html

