5.6 Inclusion/Exclusion Criteria

Inclusion Criteria:

- 1) Men and women ages 21-70,
- 2) Past-year: MDD, dysthymic disorder, generalized anxiety disorder, post-traumatic stress disorder, obsessive-compulsive disorder, or panic disorder with or without agoraphobia, based on MINI structured interview, OR Lifetime diagnosis of one of the above based on MINI with a self-report of currently receiving treatment (prescribed psychoactive medication, behavioral therapy, etc.),
- 3) Report smoking \geq 5 cigarettes per day for the past year,
- 4) Provide an intake breath CO sample >8 ppm, (if ≤ 8 ppm, then urinary-cotinine strip must be positive)
- 5) Be without current substance abuse/dependence other than nicotine,
- 6) Be sufficiently literate to complete the research-related tasks,
- 7) Be in good physical health without serious illness or change in health in the past three months as determined by the licensed medical professional at each site,
- 8) Have appropriate equipment to complete face-to-face video assessments and use iCO Smartphone Smokerlyzer Monitors. For those who do not have a Smartphone, staff will explore potential alternate plans (e.g., project-provided inexpensive Android phone)

Exclusion Criteria:

- 1) Exclusive use of roll-your-own cigarettes,
- 2) Planning to quit smoking in the next 30 days,
- 3) A quit attempt in the past 30 days resulting in greater than 3 days of abstinence,
- 4) Significant use of other tobacco or nicotine products within the past month (more than 9 days in the past 30).

- 5) Positive toxicology screen for any of the following drugs: cocaine, opiates, methadone, oxycodone, buprenorphine, benzodiazepines, barbiturates, amphetamines, methamphetamines, MDMA and PCP
 - a. Marijuana will be tested for but will not be an exclusionary criterion. Participants will be discouraged from smoking marijuana during the study.
 - b. Participants with valid prescriptions for opiates, benzodiazepines, barbiturates, or amphetamines will not necessarily be excluded.
 - c. Participants failing the toxicology screen will be allowed to re-screen once. These participants will need to be re-consented before being rescreened to ensure they have received adequate informed consent.
- 6) Self-report of binge drinking alcohol (more than 9 days in the past 30 days, 4/5 drinks in a 2 hour period in females/males),
- 7) Systolic blood pressure < 90 or ≥ 160 mmHg
 - a. Participants failing for blood pressure will be allowed to re-screen once.

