Participants will be seen weekly throughout the 16-week experimental period. Weeks 4, 8, 12, 16 and the abstinence visit will take approximately 2-4 hours each. All other sessions will last approximately 2 hours. If a participant has a positive urine or saliva toxicology test or is visibly intoxicated as determined by slurred speech, swaying, or stumbling, the session will be rescheduled until a negative test result is obtained and intoxication is not present. As a part of each experimental visit, participants will be asked to come to UHC for a product exchange. All participants must pass a COVID19 screening before entering the building. Participants will be instructed to contact the RA at the office when they get to the clinic to ensure that there is enough space in the smoking chambers to house all participants while abiding by safety guidelines as detailed on page 14 of the protocol. All participants must pass a COVID19 screening before entering the building. When invited into the lab, the participant will be shown to a smoking chamber and will be instructed to place their bag of product outside of the chamber. The participant will wait here while the RA processes and returns product through the randomization database. Then the RA will dispense new product and bring the bag back to the participant's smoking chamber and leave it on the ground in front of the chamber. When the RA deems it safe for the participant to exit the chamber, the RA will instruct the participant that they can leave. The RA will instruct the participant to observe social distancing measures during this exchange, providing clarification if necessary. At the end of each experimental session, the researcher will complete the End of Visit Evaluation Form, which will be filed in the participant's binder. This will allow the researcher to make note of any problems encountered during the visit and to assess the truthfulness of the participant in regards to self-report of tobacco use and compliance to study procedures.

Visit scheduling requirements for experimental period:

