The ideal scheduling window between each visit is 7 days based on the date of the Baseline 2 Visit. For additional scheduling requirements, refer to the '*Scheduling Visits SOP*'. If a participant misses a visit and is unable to reschedule during the window (\pm 3 days), that visit will not be 'made-up' in the future. All measures that were not completed will be considered missing data and will not be collected during future visits. If a visit mistakenly occurs outside of the designated window, this is a protocol deviation. A 'Non-Medical Event Form' will need to be completed. Additionally, each visit should occur at approximately the same time of day \pm 2 hours.

If a participant is not able to attend his/her Week 16 visit, then it should be rescheduled even if it is outside of the scheduling window. This will be documented as a protocol deviation.

7.2. Experimental Visits Weeks 1, 3, 5, 7, 9, 11, 13, and 15 Procedures

7.2.A. Measures/Assessments

Physiological Measures Collected and entered directly into REDCap by the interviewer:

- 1) CO
- 2) Blood Pressure
- 3) Heart Rate
- 4) Body temperature
- 5) Oxygen saturation
- 6) Respiratory rate
- 7) Urine or Saliva Toxicology
- 8) Urine Pregnancy test (if applicable, to be performed every 2 weeks)

The following assessments will be administered as an interview and will be entered directly into REDCap by the interviewer:

- 1) Concomitant Medications

- 2) Medical Event Form, if applicable
- 3) Health Changes Questionnaire
- 4) Time Since Last Cigarette Questionnaire

The following assessments will be completed by the participant directly in REDCap:

- 1) BDI
- 2) OASIS
- 3) COVID19 Symptom Questionnaire
- 4) Respiratory Symptom Questionnaire
- 5) MNWS
- 6) Snaith-Hamilton Pleasure Scale (SHAPS)

In the event that the REDCap website is not functioning, the assessments will be administered aloud and participant answers will be recorded securely. The interviewer will enter the data into REDCap when it resumes functioning properly. This information should be recorded in the 'End of Visit Evaluation Form'.

7.3. Experimental Visits Weeks 2, 4, 6, 8, 10, 12, 14, and 16 Procedures:

7.3.A Measures/Assessments

Physiological measures collected and entered directly into REDCap by interviewer:

- 1) CO
- 2) Blood Pressure
- 3) Heart Rate
- 4) Body temperature
- 5) Oxygen saturation
- 6) Respiratory rate
- 7) Urine or Saliva Toxicology
- 8) Urine Pregnancy test (if applicable)

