8) If a participant is discharged from or discontinues his or her methadone or buprenorphine treatment, they will be discontinued from the study.

The following will be monitored and can lead to the participant being withdrawn by the PI or Licensed Medical Professional:

- 1) Cigarettes per day increase: Continued participation will be evaluated by the site PI if the average number of cigarettes per day (CPD) increases by more than 100% from the average CPD during baseline as determined by CPD at Baseline 2.
- 2) Blood pressure (BP) or heart rate (HR) changes: If any of the following occur post-enrollment: 1) BP is at or above 160/100 or below 90/50, or 2) HR is at or above 115 bpm or below 45 bpm a manual blood pressure and heart rate measurement will be taken after 10 minutes have passed. If the manual reading is still out of range, a 'Blood Pressure and Heart Rate Symptom Checklist' and 'Medical Event Form' will be completed, and the participant will be monitored by the medical professional.
- 3) Expired breath Carbon Monoxide increase: If the average of two consecutive CO measurements meets the criteria below then the 'Medical Event Form' will be completed and the participant will be monitored by the medical professional.
 - a. CO is greater than 50 ppm if CO at Baseline 1 is <20 ppm.
 - b. CO is greater than 60 ppm if CO at Baseline 1 is 20 – 34 ppm.
 - c. CO is greater than 70 ppm if CO at Baseline 1 is 35 – 49 ppm.
 - d. CO is greater than 80 ppm if CO at Baseline 1 is 50 – 64 ppm.
 - e. CO is greater than 90 ppm if CO at Baseline 1 is 65 – 80 ppm.
- 4) Any hospitalization or debilitation in which participation in the study could be detrimental to the recovery process. This will be self-reported by the participant and will be reviewed by the site PI and medical professional to determine whether continued participation in the study is appropriate.
- 5) If a participant is behaving in an inappropriate or threatening manner, admits to lying about eligibility criteria, is participating in other smoking research studies that could affect the primary outcome measures, etc., then the PI can withdraw him/her from the study at the PI's discretion.
- 6) If a participant fails to attend regularly scheduled research assessment visits or comply with the research procedures or schedule, then the PI can withdraw him/her from the study at the PI's discretion.

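### Section 7.1 reschedules a session after any positive toxicology test, without the marijuana and prescription exemptions used at entry, so participants who stay positive lose some visit-based data by rule

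*Combined protocol and SAP*

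**What the plan says.** Section 7.1 (Experimental Period) sets the trigger, "If a participant has a positive urine or saliva toxicology test or is visibly intoxicated", and the consequence, "the session will be rescheduled until a negative test result is obtained and intoxication is not present". It names no drug and no exemption. Toxicology is listed at odd weeks (7.2.A), at even weeks (7.3.A) and in both versions of the abstinence session (7.8.A and 7.8.B).

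The panel is described only at screening (5.4), as "including up to the following drugs: marijuana, cocaine, opiates, oxycodone, benzodiazepines, barbiturates, amphetamines" and several others. The entry rules treat some positives as acceptable. On marijuana, Section 5.6 says: "Marijuana will be tested for but will not be an exclusionary criterion. Participants will be discouraged from smoking marijuana during the study". On prescriptions it says: "Participants with valid prescriptions for opiates, benzodiazepines, barbiturates, or amphetamines will not necessarily be excluded". Section 5.4 leaves prescribed medication to the investigator case by case, and Section 5.7 repeats both allowances for eligibility and the screening payment.

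The scheduling text in Section 7.1 allows 3 days either side of the target date. After that the visit is not made up: "All measures that were not completed will be considered missing data and will not be collected during future visits". Week 16 is the exception and is rescheduled even outside the window, as a protocol deviation. Section 7.8 places the abstinence session 18 to 30 hours after the Week 16 visit.

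**The concern.** Taken together, the passages admit people who may test positive throughout the trial and then block their sessions until they test negative. Someone on a continuing prescription for a panel drug, or who keeps using marijuana, may not turn negative within the window. Missing data then follow from a written rule and not from anything the participant failed to do.

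The measures exposed are those collected at or after the toxicology step. They include CO and the urine biomarkers of toxicant exposure, which are named Aim 2 outcomes, and the abstinence-session data that make up Aim 3. Section 9.1 plans to use all available data without imputation if data are missing at random. It does not mention loss linked to toxicology status. CO and biomarker results would then lean towards participants who test negative, a narrower group than the one enrolled.

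**Working it through.** 1. **Does any exemption reach the experimental visits?** The allowances appear in 5.4, 5.6 and 5.7, and each concerns screening, eligibility or the screening payment. Section 7.1 neither repeats nor cross-refers to them. Advice that only discourages marijuana during the study presumes that some participants will continue.

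2. **What is lost at Weeks 1-15?** A session first attempted on its target day leaves 3 further days to obtain a negative test. One attempted at the earliest permitted day leaves 3 + 3 = 6. A participant positive throughout loses the visit. The no-make-up rule covers 15 of the 16 weekly visits, so 15 is the worst case from that rule alone.

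3. **Which measures?** Section 6 fixes the order for Baseline 1 and all later visits. Participant-completed questionnaires come first and are reviewed by staff, then the physiological portion by video, then exchange of product and samples. Toxicology belongs to the physiological portion. The depression, anxiety, withdrawal, craving, dependence and purchase-task forms are participant-completed, so they normally exist before the result is known. Exposed are CO and the other readings of the stopped session, the interviewer-administered forms, and samples handed over afterwards.

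4. **Biospecimens.** Urine and saliva are collected at Baseline 2, Week 8 and Week 16. A blocked Week 8 visit costs 1 of 2 post-baseline collections. Participants collect these samples with equipment supplied at the previous visit, so the sample may exist and still not be accepted.

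5. **Week 16.** The window does not make it missing. It is delayed, and lost only if a negative result never comes.

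6. **Abstinence session.** The window is 30 - 18 = 12 hours wide, so waiting for a negative test is barely feasible. Section 7.1 mentions this visit in the same paragraph as the rescheduling rule. The questionnaire set here depends on whether CO is at or below 6 ppm, so CO must be known before the right set is chosen, and the usual questionnaires-first order gives less protection.

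7. **Relation to the sample size (9.2).** The stated 53 per condition reproduces. A two-sample t-test at effect size 0.60, two-sided 0.05 and 80% power needs 44.6, so 45 evaluable per arm; 45 / (1 - 0.15) = 52.9, so 53. That calculation is for CPD, which comes from daily interactive voice response (IVR) calls (7.4), so it is not directly affected. For a visit-based measure, let m be the share of evaluable participants lacking it because of the rule. The documents give no m, so the values below are assumptions that show scale only, at the same effect size:

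| m | Evaluable per arm, 45 x (1 - m) | Pairwise power |
|---|---|---|
| 0 | 45 | 80% |
| 5% | 42.8 | 78% |
| 10% | 40.5 | 76% |
| 20% | 36.0 | 71% |
| 30% | 31.5 | 65% |

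Section 9.2 reports an observed effect size of 0.33 for breath CO, below 0.60, so CO has little precision to spare.

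**The case against.** The best defence is that the literal reading is not the intended one. The protocol uses a positive test as shorthand elsewhere. Section 7.9 says without qualification that a second positive means exclusion, although 5.4 and 5.6 exempt marijuana and prescriptions from the same rule. Staff would probably carry the exemptions forward, and a scheduling SOP not included in the documents may say so. Admission with a prescription is case by case, the panel is described as up to the listed drugs, and the medical professional may decline anyone unlikely to complete. The affected group could be small. All of this stands as a limit on size. It does not remove the conflict: the written rule is unconditional, and two sites could apply it differently.

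Some stronger inferences are tempting but unsupported:

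- **The main outcome goes missing.** CPD is reported daily by IVR, outside the visits.
- **Self-report scales are lost.** They normally precede the test. The gap is that the plan does not say whether answers from a stopped session are kept or repeated.
- **Participants run out of study cigarettes and smoke others.** A 14-day supply at 150% is 14 x 1.5 = 21 days at the baseline rate, and 8.4 allows unscheduled visits for more.
- **A planned moderator is distorted.** The medication moderator in 9.1 is SSRI versus non-SSRI antidepressant, and antidepressants are not on the panel.
- **The comparison between conditions is biased.** Prescriptions and marijuana use at entry precede randomisation and should balance. What is shown is loss of precision and of coverage of the enrolled population.
- **Affected participants will be withdrawn.** Section 13 covers the case "If a participant fails to attend regularly scheduled research assessment visits or comply with the research procedures or schedule", but there the investigator may withdraw and need not.

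**Conclusion.** The point holds in limited form. Followed as written, Section 7.1 costs a participant who stays toxicology-positive CO and the interviewer-administered measures at up to 15 weekly visits, one of two post-baseline urine and saliva collections, and probably the abstinence session. Week 16 is delayed, and lost only without any negative test.

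This rests on three assumptions: that staff apply the rule literally, that the participant remains positive through each window, and that readings from a stopped session do not count for the visit (CO is listed before toxicology, but no sequence or retention rule is given). The documents say nothing on how many participants this describes, so no overall loss can be stated. The correction is worth making because the loss is avoidable and samples not taken in the window cannot be recovered. It does not threaten the CPD analysis.

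**What to change.** Reconcile Sections 5.4, 5.6, 5.7, 7.1 and 7.8 so that the post-enrolment rescheduling rule is consistent with the entry criteria. The protocol team should decide and write down which positive results trigger rescheduling, and whether this applies to the abstinence session. In addition:

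- record the toxicology result at every visit, including stopped ones;
- state that questionnaires completed before a session is stopped are kept for that visit;
- state that the self-collected Week 8 and Week 16 urine and saliva are accepted within the window even when the session is stopped.

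The cost is a few sentences in the protocol and a matching change to the visit SOP. The small downside is that some data will come from toxicology-positive participants. The recorded result allows a sensitivity analysis with and without them.

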To our knowledge, we are the first to report the effects of reduced-nicotine cigarettes on measures of cigarette reinforcement in smokers with ADs. In Study 1, we examined the acute subjective and behavioral effects of cigarettes varying in nicotine content (15.8, 5.2, 2.4 and 0.4 mg nicotine/g tobacco) in smokers with ADs.^{9,10} In concurrent choice testing with the cigarettes available at an equal response effort, participants chose the higher over the lower nicotine content cigarettes across each of the six dose pairs consistent with reduced nicotine content cigarettes having lower addiction potential (below, left). The only difference between populations was at the 0.4 versus 2.4 mg/g dose pair, where smokers with affective disorders chose the higher dose more often ($p < .001$), while disadvantaged women ($p = .06$) and those with opioid dependence ($p = .91$) did not exhibit a significant preference between those two doses (below, right). All doses decreased craving and withdrawal symptoms with no evidence of compensatory smoking. While the higher nicotine cigarettes were rated as more satisfying, increasing the response requirement to obtain these cigarettes reversed that preference. This observation has considerable tobacco regulatory implications. For example, allowing VLNCCs to be sold in common retail outlets while restricting sale of higher content cigarettes to more regulated stores would be predicted to shift preference towards the former. This same concept may also extend to regulatory efforts to shift preference from harmful combusted to less harmful non-combusted tobacco products. Overall, our results indicate that reducing the nicotine content of cigarettes reduces the relative reinforcing effects of smoking, and hence addiction potential, in smokers with ADs and other vulnerabilities to tobacco addiction. The 0.4 mg/g most robustly differed from the 15.8 mg/g dose in this population, supporting prior hypotheses about reducing nicotine content below 0.7 mg/g³.

In Study 2, we are examining effects of cigarettes varying in nicotine content in smokers with ADs over a 12-week period. Preliminary results from 35 participants indicate that VLNCCs reduce smoking rates by >40% relative to NNCCs in Weeks 9-12 (see figure at right). However, while smokers with ADs reduce their smoking rates, few quit completely, similar to results seen in

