After the week 16 visit, participants will be required to attend one additional visit the following day. During this visit, participants will have been encouraged to abstain from smoking until their next scheduled visit (approximately 24 hours later). The abstinence assessment session should be scheduled no less than 18 hours and no more than 30 hours after the Week 16 visit. Abstinence will be verified by an expired breath carbon monoxide level of less than or equal to 6 parts per million (ppm). This session will allow us to determine whether the experimental cigarettes and e-cigarette use (for the e-cigarette conditions) have reduced the effects of abstinence on these measures relative to the control conditions. If the participant does NOT meet abstinence criteria, he/she will only receive \$20 for the visit. Those who do meet abstinence criterion will do concurrent choice session

detailed below.

7.8.A Participants Who Meet Criteria for Abstinence

7.8.A.1 Measures/Assessments

Physiological measures collected and entered directly into REDCap by the interviewer at the end of the visit:

- 1) CO
- 2) Blood Pressure
- 3) Heart Rate
- 4) Body temperature
- 5) Oxygen saturation
- 6) Respiratory rate
- 7) Urine or Saliva Toxicology

The following assessments will be administered as an interview and will be entered directly into REDCap by the interviewer:

- 1) Concomitant Medications
- 2) Medical Event Form, if applicable
- 3) Health Changes Questionnaire
- 4) Time Since Last Cigarette Questionnaire

The following assessments will be completed by the participant directly in REDCap:

- 1) BDI
- 2) OASIS
- 3) COVID19 Symptom Questionnaire
- 4) Respiratory Symptom Questionnaire
- 5) MNWS
- 6) PANAS
- 7) QSU-brief - Usual Cigarette
- 8) QSU-brief - Study Cigarette
- 9) Vaping Craving Questionnaire
- 10) Cigarette Purchase Task - Usual Brand Cigarette Version
- 11) Cigarette Purchase Task - Study Cigarette Version
- 12) E-cigarette Purchase Task- E-cigarette Version
- 13) Snaith-Hamilton Pleasure Scale (SHAPS)

In the event that the REDCap website is not functioning, the assessments will be administered aloud and participant answers will be recorded securely. The interviewer will enter the data into REDCap when it resumes functioning properly. This information should be recorded in the 'End of Visit Evaluation Form'.

7.8.B. Participants Who Do Not Meet Criteria for Abstinence

7.8.B.1 Measures/Assessments

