Participants can receive up to \$120.00 for the abstinence session (\$20 if participant does not achieve abstinence, \$120 if participant reaches abstinence), \$40 for biochemical verification of abstinence at 30 day follow up visit, and up to \$306 for completing daily IVR reports of study cigarette and other nicotine and tobacco use. There will also be a \$150 bonus distributed at Week 16 for completing the study. Participants who do not complete the entire study will receive compensation for the sessions that they do complete. Total compensation for completing Study 3, including study visit payments, daily IVR calls and end of study bonus is \$2816. As mentioned above, participants will have a chance to earn additional incentives for compliance, honesty and attendance through urine testing. Participants will be given a debit card at the beginning of the study (during the second portion of the screening visit) and compensation for each visit will be automatically transferred to the card after they complete that visit. If debit cards are unavailable, participants will be paid via an alternate method (i.e. cash or check).

7.10. End of Study:

After a participant has completed all study procedures and has been paid for participation the research assistant will read the following script and give the participant the *Clearing the Air*

Manual.

"If you've reduced your smoking during this study, we encourage you to continue these reductions or even consider quitting. We would like to provide you with some resources should you decide to try to abstain from smoking (give "Clearing the Air" and hotline information). Please also feel free to consult with your physician and use any medications he/she deems appropriate. We will call you in approximately 30 days to ask about your smoking since leaving the study. There is no right answer and we know how difficult quitting can be. Please just answer honestly. The call will take less than 5 minutes. Thanks again for your participation."

The following assessments will be administered using REDCap:

- 1) End of Study Questionnaire

7.11. 30 Day Follow up Phone Call:

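### Section 7.8 verifies abstinence by breath CO of 6 ppm or less alone, although smokers with CO that low can enrol; adding self-report and the Week 16 CO would protect exploratory Aim 3 cheaply

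*Combined protocol and SAP*

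**What the plan says.** **Entry (Section 5.6).** Inclusion 3 asks for at least 5 "cigarettes per day for the past year". Inclusion 4 asks for an intake CO above 8 ppm, but also accepts 8 ppm or less, in which case "then urinary-cotinine strip must be positive". No lower CO limit is given.

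**Abstinence session (Section 7.8).** The test is: "Abstinence will be verified by an expired breath carbon monoxide level of less than or equal to 6 parts per million (ppm"). On timing: "The abstinence assessment session should be scheduled no less than 18 hours and no more than 30 hours after the Week 16 visit". The "Time Since Last Cigarette Questionnaire" is listed in 7.8.A, for those who have met the criterion. It does not help decide who meets it, and it is not listed in 7.8.B for those who fail.

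**What the criterion controls.** Those who pass complete the withdrawal (MNWS), affect (PANAS), craving (QSU) and purchase-task measures (7.8.A). Those who fail do not (7.8.B). Passing pays $120 rather than $20 (Section 7.9).

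**Use of the data.** Aim 3 is exploratory and concerns demand, craving and withdrawal during abstinence (Section 1). It is analysed by ANCOVA on this single visit (Section 9.1), with no stated check of abstinence status.

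**Follow-up (Section 7.11).** At the 30-day call, CO verification against the same 6 ppm limit is offered only to participants who first report being abstinent.

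**The concern.** In a person whose CO is 6 ppm or less while smoking, this test cannot tell smoking from abstinence. Such people are eligible under inclusion 4. Others may reach that level during the trial, because the plan hypothesises a graded fall in CO across conditions by Week 16 (Section 1).

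Aim 3 is meant to describe craving, withdrawal and demand when participants are not smoking. Someone who has smoked recently would be expected to score lower on craving and withdrawal; Section 3.1 reports that every nicotine dose in the earlier acute study reduced both. If undetected smoking is more common where CO has fallen most, the very low nicotine and e-cigarette conditions would appear to ease abstinence effects partly because more of their supposed abstainers had smoked.

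**Working it through.** **Side-by-side reading**

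| Point | Section | CO rule | Self-report needed? |
|---|---|---|---|
| Entry | 5.6 | above 8 ppm, or 8 ppm or less with a positive cotinine strip | at least 5 cigarettes a day |
| Week 16 visit | 7.3.A | CO measured, not used in 7.8 | not applicable |
| Abstinence session | 7.8 | 6 ppm or less | no |
| 30-day follow-up | 7.11 | 6 ppm or less | yes, before CO |

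1. The entry rule and the abstinence rule overlap only at 0 to 6 ppm. A participant whose CO while smoking is 7 or 8 ppm can enrol but would fail the session test if still smoking.
2. Within 0 to 6 ppm nothing in 7.8 separates a smoker from an abstainer.
3. The 30-day follow-up pairs self-report with CO; 7.8 uses CO alone.
4. The plan gives no figure for how many smokers have CO of 6 ppm or less, so it has no stated number to reproduce.

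**Illustration under assumed inputs**

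Let a be the share of attendees who truly abstain (assumed 0.3 to 0.7, all taken to pass). Let f be the share of non-abstainers whose CO while smoking is 6 ppm or less (assumed 0 to 0.20). Neither is in the documents.

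False share among the verified = (1 − a)f / [a + (1 − a)f].

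- f = 0: 0%, whatever a is.
- a = 0.5, f = 0.05: 0.025 / 0.525 = 4.8%.
- a = 0.5, f = 0.10: 0.05 / 0.55 = 9.1%.
- a = 0.5, f = 0.20: 0.10 / 0.60 = 16.7%.
- a = 0.7, f = 0.05: 0.015 / 0.715 = 2.1% (lowest result with f above zero).
- a = 0.3, f = 0.20: 0.14 / 0.44 = 31.8% (highest).

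With 53 per condition and the 15% loss stated in Section 9.2, about 53 × 0.85 = 45 attend. The number falsely verified is 45(1 − a)f. With f above zero this runs from 45 × 0.3 × 0.05 = 0.7 to 45 × 0.7 × 0.20 = 6.3 people per condition.

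**What unequal misclassification would do.** Suppose a = 0.5 in two conditions, with f = 0.05 in one and f = 0.20 in the other. The false shares differ by 16.7% − 4.8% = 11.9 percentage points. If smoking rather than abstaining lowers a mean withdrawal score by D in both conditions, the comparison shifts by about 0.12 × D with no true condition effect. This shows the direction and the mechanism; it does not estimate the size in this trial.

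**The case against.** **The frequency is unknown.** A reader might infer that some participants will certainly be verified while smoking. The documents do not show this: they give no CO distribution, and the number could be zero.

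**Entry CO is not a fixed trait.** A reader might infer that everyone admitted at 8 ppm or less, or at 6 ppm or less, can pass without abstaining. The first group is too wide, because the limit is 6 ppm. The second treats one screening value as the person's usual level 16 weeks later, although a low reading may only reflect a long gap since the last cigarette.

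**The affected group cannot be extended by arithmetic.** Section 3.1 reports that "VLNCCs reduce smoking rates by >40% relative to NNCCs in Weeks 9-12". A reader might multiply entry CO by 0.6 and conclude that smokers entering at up to 10 ppm pass in the very low nicotine arms (10 × 0.6 = 6.0), or at up to 15 ppm with an assumed 60% fall in an e-cigarette arm (15 × 0.4 = 6.0). These boundaries are not supported. The figure is a preliminary between-group difference in 35 participants, not a fall from a person's own baseline. CO also need not fall in proportion to cigarettes: Table 2 gives an effect size of 0.81 for cigarettes per day and 0.33 for CO. Standardised effects do not convert to ppm, but they lend no support to proportionality.

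**The data exist already.** Week 16 CO is collected, Time Since Last Cigarette is recorded in those who pass, and daily telephone reports of smoking run through the experimental period (Section 7.4). Discordant cases could be found afterwards. This stands, but no rule says how these data would be used.

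**CO is a defensible marker.** Cotinine cannot show abstinence from smoking in participants supplied with nicotine e-cigarettes. This also stands; the weakness is using CO with nothing beside it.

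**The stakes are limited.** Only exploratory Aim 3 and a payment are affected.

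**Conclusion.** The point holds as a cheap improvement. The rule in 7.8 can class a continuing smoker as abstinent when that person's CO while smoking is 6 ppm or less, and the entry criteria do not keep such people out. Misclassification may be more frequent in the very low nicotine and e-cigarette conditions. That inference rests on the plan's own hypothesis about CO and on recent smoking lowering craving and withdrawal scores. If both hold, the bias in Aim 3 favours those conditions.

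The size cannot be determined from the documents. The 0% to 31.8% range reflects assumed inputs only. The primary cigarettes-per-day outcome and Aim 2 do not depend on this criterion, and the 30-day follow-up already requires self-report first.

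**What to change.** 1. **Reconcile the abstinence period.** Section 1 describes incentives to abstain during a three-hour laboratory session in Week 17. Section 7.8 describes about 24 hours of abstinence before a visit on the day after Week 16. The definition below needs one stated period.
2. **In 7.8, ask Time Since Last Cigarette of all attendees before the CO criterion is applied.**
3. **For the Aim 3 analysis, define verified abstinence** as CO of 6 ppm or less plus self-report of no cigarette over the reconciled period.
4. **Report by condition** how many participants had a Week 16 CO of 6 ppm or less. For them the session CO carries little information about abstinence.
5. **Repeat the Aim 3 comparison without those participants**, as a sensitivity analysis only. It excludes people on a value measured after randomisation that the conditions may themselves affect.

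**Cost.** A short text change in 7.8, one questionnaire moved earlier and asked of everyone, one table by condition and one extra analysis run; no new test. There will be fewer verified abstainers. Self-report may also be misreported when participants believe that $100 ($120 − $20) depends on it. The Week 16 CO sensitivity analysis covers this in part, because it does not rely on self-report.
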